Background	
The Cardioband Transcatheter System (Cardioband) is indicated for the treatment of secondary (functional) mitral regurgitation (FMR). The Cardioband is a transcatheter system, deployed on the beating heart through a transseptal approach. The Cardioband is deployed along the posterior annulus of the mitral valve and is adjusted under trans-esophageal guidance on the beating heart. 

Hypothesis	
 1) The Cardioband will reduce the severity of MR acutely with durable performance at 6 months 2) The Cardioband will improve 6 minute walk test at 6 months 3) The Cardioband will improve heart failure associated quality of life at 6 months
Objectives	
 1) To test the efficacy of the Cardioband in improving MR and heart failure symptoms in patients with symptomatic (NYHA Class III-IVa), severe MR in the post-marketing setting 2) To evaluate the safety of the Cardioband system in the post-marketing setting
Study design	
A multi-center (up to 20 sites) single arm open label study in n = 50 subjects. Subjects will be followed for up to 2 years.

Subject Population	
Patients with secondary (functional) MR, symptomatic (NYHA Class III-IVa heart failure symptoms), with severe MR and to whom The Local Site Heart Team concur that surgery will not be offered as a treatment option and that medical therapy is the intended therapy.

Endpoints	
Primary Endpoint (powered): Reduction in severity of MR at 30 days of at least one category on a 0-4 scale.
 
Key Secondary Endpoint (powered): Change in 6 minute walk test at 6 months.
 
Secondary Endpoints (all at 6, 12, and 24 months except as indicated) :
 
 1) MR severity 2) 6 minute walk distance 3) Quality of life as assessed by the Kansas City Cardiomyopathy Questionnaire (KCCQ) (also at 30 days) 4) NYHA Class (also at 30 days) 5) Left Ventricular End Diastolic Volume (LVEDV) 6) Left Ventricular End Systolic Volume (LVESV) 7) Device success defined as deployment of the Cardioband, with MR reduction at hospital discharge. 8) Individual patient success (6 months and 1 year) defined as device success and the following:

	REPAIR - Transcatheter REPAIR of Mitral Insufficiency with CaRdioband System Post Market Study Protocol ID CB1-3	
---	---	---

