	
 • Discharged from index hospitalization • NYHA class improvement by at least 1 level from baseline 
9) Days alive and out of hospital (due to major cardiovascular events) at 1 year
 
10) Freedom from all-cause mortality and major adverse events defined as disabling stroke, myocardial infarction (peri-procedural or spontaneous), renal failure requiring dialysis, life-threatening bleeding, cardiac tamponade and device related cardiac surgical intervention at 30 days from the implant procedure or hospital discharge, whichever is later. (Individual components will also be evaluated).
 
11) Need for urgent/emergent surgical intervention

Sample Size Considerations	
Based on the results of the Cardioband CE mark study (Protocol ID CB 1-2), the present study with a sample size of 50 subjects will have greater than 80% power to detect a reduction in MR severity of at least one grade (CE mark study showed improvement in MR severity of at least one grade in >80% of subjects in CE mark study).
 
Based on the results of the Cardioband CE mark study (Protocol ID CB 1-2), the present study with a sample size of 50 subjects will have greater than 90% power to detect an improvement of 75 m in 6 minute walk test at 6 months (CE Mark study showed an improvement of 93.3 m ± 90.3 m).

Inclusion Criteria	
 1) Age ≥18 years 2) Severe (3+ to 4+) secondary Mitral Regurgitation 3) Symptomatic heart failure (NYHA Class III-IVa) despite guideline directed medical therapy including CRT if indicated 4) The Local Site Heart Team concur that surgery will not be offered as a treatment option and that medical therapy is the intended therapy. 5) Transfemoral access and transseptal deployment of the Cardioband is determined to be feasible 6) Subject is willing and able to provide informed consent and follow protocol
Exclusion Criteria	
 1) EF < 20% 2) LVEDD ≥ 70 mm 3) Heavily calcified annulus or leaflets 4) Significant CAD requiring revascularization 5) Active bacterial endocarditis 6) Any percutaneous coronary, carotid, endovascular intervention or carotid surgery within 30 days or any coronary or endovascular surgery within 3 months 7) Renal insufficiency requiring dialysis

	REPAIR - Transcatheter REPAIR of Mitral Insufficiency with CaRdioband System Post Market Study Protocol ID CB1-3	
---	---	---

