9.2 Appendix 2 – Reportable Events - by MVARC

The following is a list of events defined by MVARC as clinical endpoints to be collected in all trials of mitral valve therapies. The different events should be reviewed and reported in light of the following definitions.

[figure not shown]

Mortality
	
 1. Cardiovascular vs. non-cardiovascular mortality 
 a. Cardiovascular mortality - Any of the following contributing conditions: 
 • Heart failure (subclassified into left ventricular vs. right ventricular dysfunction) • Myocardial infarction • Major bleeding • Thromboembolism • Stroke • Arrhythmia and conduction system disturbance • Cardiovascular infection and sepsis (e.g., mediastinitis and endocarditis) • Tamponade • Sudden, unexpected death • Other cardiovascular • Device failure • Death of unknown cause (adjudicated as cardiovascular) b. Non-cardiovascular mortality - Any death in which the primary cause of death is clearly related to another condition: 
 • Non-cardiovascular infection and sepsis (e.g., pneumonia) • Renal failure • Liver failure • Cancer • Trauma • Homicide • Suicide • Other non-cardiovascular 2. Periprocedural vs. non-periprocedural mortality: 
Death is considered periprocedural if occurring within 30 days of the intervention or beyond 30 days in the patient not yet discharged

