Specific device-related technical failure issues and complications	
Technical failure (measured at exit from the catheterization laboratory):
 
 1. Procedural mortality; 2. Failure in access, delivery, or retrieval of the device delivery system; 3. Failure in deployment and correct positioning of the first intended device; 4. Emergency surgery or reintervention related to the device or access procedure. 
Device failure (measured at 30 days and at all later post-procedural intervals)
 
 1. procedural mortality or stroke; or 2. failure in placement and positioning of the device; or 3. unplanned surgical or interventional procedures related to the device or access procedure; or 4. lack of safety and performance of the device, including: 
 • evidence of structural or functional failure • device-related technical failure issues and complications • significant mitral stenosis 
Procedural Failure (measured at 30 days)
 
 1. Device failure 2. major device or procedure related serious adverse events, including: 
 • Death • Stroke • Life-threatening bleeding (MVARC scale) • Major vascular complications • Major cardiac structural complications • Stage 2 or 3 acute kidney injury (includes new dialysis) • Myocardial infarction or coronary ischaemia requiring PCI or CABG • Severe hypotension, heart failure, or respiratory failure requiring intravenous pressors or invasive or mechanical heart failure treatments such as ultrafiltration or hemodynamic assist devices, including intra-aortic balloon pumps or left ventricular or biventricular assist devices, or prolonged intubation for ≥ 48 h. • Any valve-related dysfunction, migration, thrombosis, or other complication requiring surgery or repeat intervention

	
REPAIR - Transcatheter REPAIR of Mitral Insufficiency with CaRdioband System Post Market Study Protocol ID CB1-3
	
---	--	---

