	
Patient failure (measured at 1 year)
 
 1. Device failure 2. Patient returned to the pre-procedural setting 3. rehospitalizations or reinterventions for the underlying condition (e.g., mitral regurgitation, heart failure); 4. No Improvement from baseline in symptoms (e.g., no NYHA improvement by ≥ 1 functional class); and 5. No Improvement from baseline in functional status (e.g., 6-min walk test did not improve by ≥ 50 m); and 6. No Improvement from baseline in quality-of-life (e.g., no improvement in Kansas City Cardiomyopathy Questionnaire by at least ≥ 10) 
*MR reduction is considered optimal when post-procedure MR is reduced to trace or absent. MR reduction is considered acceptable when post-procedure MR is reduced by at least 1 class or grade from baseline and to no more than moderate (2+) in severity. For clinical trials and registry studies, assessment of baseline and post-procedure MR must be made by an echocardiographic core laboratory. For large observational databases, baseline and post-procedure MR may be assessed by physicians trained in echocardiography evaluation.

--	---

Mortality, Hospitalization, Neurological events and Myocardial Infarction are events which should be adjudicated by an independent central adjudication committee.

For further details for each event, please refer to The Mitral Valve Academic Research Consortium (MVARC) Guidelines: Clinical Trial Design Principles and Endpoint Definitions for Transcatheter Mitral Valve Repair and Replacement (JACC 2015;66(3):278-307).

- Document End -

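### Does the un-negated second item in the Appendix 2 patient-failure list undermine the 1-year success endpoint?

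*Combined protocol and SAP*

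**What the plan says.** Two separately named constructs apply at 1 year.

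- **Endpoint 8** (Synopsis; Section 3.2.3) is introduced as "Individual patient success (6 months and 1 year) defined as device success and the following". Its conditions are discharge from the index stay and "NYHA class improvement by at least 1 level from baseline". Device success is endpoint 7 and is judged at hospital discharge. The Synopsis shows the two conditions as sub-bullets; Section 3.2.3 numbers them 9 and 10 as if they were endpoints, which is a clerical slip.
- **Patient failure** (Appendix 2, in the row on device-related technical failures and complications) has six items: (1) device failure, (2) "Patient returned to the pre-procedural setting", (3) rehospitalisation or reintervention for the underlying condition, (4) no gain in symptoms, (5) no gain in walk distance, (6) no gain in quality of life.

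Nothing joins items 1 to 3. Items 4 and 5 each end in a conjunction, as in "No Improvement from baseline in symptoms (e.g., no NYHA improvement by ≥ 1 functional class); and". The device-failure list in the same row uses the other one: "failure in placement and positioning of the device; or".

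On the standing of the appendix, Section 7.1 cites it for adverse event definitions. Its own lead-in calls the entries clinical endpoints that trials of mitral therapies should gather, and adds: "The different events should be reviewed and reported in light of the following definitions".

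**The concern.** Items 4 to 6 are phrased as the absence of a benefit, and items 1 and 3 are bad events. Item 2 alone sounds like recovery: the patient went back to where he or she lived before the procedure. If each of items 1 to 3 is sufficient, going home makes a patient a failure. If all six are required, a patient who never got home cannot be one. Neither result looks intended.

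The two constructs also differ in content. Endpoint 8 at 1 year fixes device success at discharge and does not look at later readmission or reintervention. Appendix 2 counts those events, and assesses device failure from 30 days onward. Nothing in the documents relates the two constructs. At stake would be a reported 1-year failure rate that cannot be derived in one way only, and that may sit beside a success rate covering some of the same patients.

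**Working it through.** The plan gives no figure to reproduce here, and no alpha, power, standard deviation or drop-out input enters. The check is logical: can one patient be both an endpoint 8 success and a patient failure, and what does the answer depend on?

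**Step 1: successes who returned to the earlier setting.** Endpoint 8 requires a NYHA gain, so item 4 is false. Items 1, 3, 5 and 6 are free, which gives 2 × 2 × 2 × 2 = 16 patterns. The table counts how many are also patient failures.

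| Rule for the six items | Item 2 as printed (true) | Item 2 reversed (false) |
|---|---|---|
| 1 or 2 or 3 or (4 and 5 and 6) | 16 | 16 − (2 × 2) = 12 |
| any of 1 to 6 | 16 | 16 − 1 = 15 |
| (1 and 2 and 3) or (4 and 5 and 6) | 1 × 1 × 2 × 2 = 4 | 0 |
| all of 1 to 6 | 0, as item 4 is false | 0 |

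The two values of 16 are partly built in: the patients were chosen because item 2 is true, and the rule makes item 2 sufficient. The trouble-free patient (items 1, 3, 5 and 6 all false) is a failure under the first two rules as printed, and under no rule once item 2 is reversed.

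**Step 2: all endpoint 8 successes, returned or not.** Return is now free as well, so there are 2 × 16 = 32 patterns.

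- Any of six: exactly one pattern escapes, so 32 − 1 = 31 overlap, whether item 2 is printed or reversed.
- 1 or 2 or 3 or (4 and 5 and 6): the escapes need items 1, 2 and 3 all false with 5 and 6 free, which is 2 × 2 = 4. So 32 − 4 = 28 overlap, again with either version.
- All six: 0 with either version.

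Reversing item 2 therefore rescues the trouble-free patient but leaves the amount of overlap unchanged. The rest comes from the constructs measuring different things, which no rewording of item 2 would remove.

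**Step 3: is endpoint 8 left undefined?** It is not. Its three components are stated in full, none refers to Appendix 2, and its timing is given. An analyst can compute it without opening the appendix.

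**Step 4: does any result use patient failure?** None in the published text. It is absent from Section 3.2 and from the endpoint list in the Synopsis. The statistical rationale in Section 6.2 covers only MR reduction at 30 days and the 6-minute walk at 6 months. Table 1 has no field for patient failure, and the note closing Appendix 2 does not name it among the events for central adjudication.

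**Step 5: are the later events hidden?** They are not. The secondary endpoints include days alive outside hospital at 1 year and urgent or emergent surgery. NYHA class, walk distance, KCCQ and MR severity are each reported at 12 months, so a reader sees the content of items 4 to 6 and much of item 3 directly.

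**The case for a change.** The best case for acting is that Appendix 2 is operative text: Section 7.1 invokes it, and its lead-in says events are to be reported by its definitions. Sufficiency of each of items 1 to 3 is a natural reading, because the neighbouring technical-failure list also lacks conjunctions and a procedural death alone must surely qualify there. Section 6.3.4 foresees further structural heart treatment without saying how such a patient is classed under endpoint 8. Clarification would cost a few lines, and settling the rule early would prevent a choice made after results are seen.

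Part of this stands: item 2 is ambiguous, and the combination rule is incomplete. The remainder does not carry the point.

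- The obvious rewording is not shown to be right. Item 2 may mean relapse to the pre-procedural state, which is a failure as worded. Items 1 and 3 are also un-negated, because they are bad outcomes already.
- The only conjunction printed between items of this list is the one that joins items 4 to 6. Carried through the list, it gives no overlap with endpoint 8.
- Appendix 2 refers readers to the MVARC guideline for further detail on each event. That source was not available here, so the ambiguity is established only for the reproduced text.
- Handling of additional treatment under Section 6.3.4 is a separate question that Appendix 2 wording would not answer.
- Judging device success at discharge is an explicit choice, and later events are largely visible through other endpoints.

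**Conclusion.** No change to the plan follows. The wording is loose, but it sits in a reporting appendix and concerns a construct that is neither an endpoint nor part of a stated analysis. Endpoint 8 is computed from Section 3.2.3 and needs no tie-break. Two differently named measures with different content may disagree about a patient without contradicting each other.

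In size, the overlap with endpoint 8 runs from 0 of 32 logical patterns (all six items required) to 31 of 32 (any one sufficient), and reversing item 2 moves neither figure. The documents give no rates, so nothing can be said about how many patients would be affected. The effect on the primary endpoint, the key secondary endpoint and the sample size is nil.

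This rests on two assumptions: that endpoint 8 is analysed as Section 3.2.3 defines it, and that anyone who tabulates Appendix 2 patient failure shows its items separately or states the reading used. Both are ordinary practice. A formal clarification, or an extra count of readmissions among successes, would put that practice in writing without altering a stated result.
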